5.5.2 Dispensing the study treatment

The investigational drug, VAY736 will be prepared by Novartis and supplied to the unblinded pharmacist / technician at the Investigator's site as open labeled bulk medication of several 6 mL glass vials.

For preparation of the study medication, a copy of the randomization list will be sent to the unblinded pharmacist / technician at the Investigator's site.

Clinical supplies are to be dispensed only in accordance with the specified study procedures. Appropriate documentation of the subject specific dispensing process must be maintained.

Bulk medication labels will be in the local language, will comply with the legal requirements of each country, and will include storage conditions for the drug but no information about the subject.

5.5.3 Handling of study treatment

5.5.3.1 Handling of investigational treatment

Investigational treatment must be received at the study site by a designated person, handled and stored safely and properly, and kept in a secured location to which only the Investigator and designated staff have access. Upon receipt, the study drugs should be stored according to the instructions specified on the labels.

Storage conditions (2-8°C) must be adequately monitored and appropriate temperature/logs maintained as Source data.

The unblinded pharmacist and Investigator are accountable for ensuring maintenance of an accurate record of the shipment and dispensing of study drug in a drug accountability ledger. Drug accountability will be noted by the unblinded Monitor during site visits and/or at the completion of the trial.

All drug supplies are to be used only for this protocol and not for any other purpose. Unless specifically instructed by Novartis, the Investigator must not destroy any drug labels, or any partly used or unused drug supply.

At the conclusion of the study, and, if allowed during the course of the study (e.g. an open label study or an unblinded monitor), the Investigator will provide a copy of the drug accountability ledger to the Monitor.

Only after receiving a written authorization by Novartis, the Investigator/designee will send all the unused and partly used drug supplies as well as the empty containers to the address provided at the time of authorization for destruction or have the unused and partly used drug supplies as well as the empty containers destroyed by the site's pharmacist, providing a drug destruction certificate.

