5.1 Protocol requested treatment

5.1.1 Investigational treatment

The investigational drug, VAY736 will be packed by Novartis and supplied to the Investigator as open labeled bulk medication. The dosage form of the supplied drug is lyophilizate in vial and needs to be reconstituted with water for injection (USP or equivalent) and diluted in 5% dextrose infusion bag (USP or equivalent), both provided by the investigator's site. Please refer to [Table 5-1](#) for VAY736 formulation information.

The placebo control selected for this study is the 5% dextrose solution in the infusion bag.

Table 5-1 Study drug: VAY376

Name	VAY736	Placebo
Formulation	Powder for solution for infusion (lyophilizate in vial)	NA
Appearance before reconstitution	White lyophilized cake	NA
Appearance after reconstitution	Opalescent to clear, colorless solution	NA
Unit dose	150 mg per vial*	NA
Packaging	6 mL Type I glass vials	NA
Diluent for IV administration	Dextrose 5% in water (USP or equivalent) in 250 mL	Dextrose 5% in water (USP or equivalent) in 250 mL

* The vials contain a 20% overfill to allow a complete withdrawal of the labeled amount of VAY736

Clinical supplies are to be dispensed only in accordance with the specified study procedures.

An unblinded pharmacist or authorized designee is required to prepare the study drug. Instructions for storage and handling of VAY736 vials, and preparation of VAY736 and placebo infusions are described in the VAY736 Pharmacy Manual (or Dose Preparation Manual), provided as a separate document.

Of note, VAY736 vials require storage between 2-8°C.

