5.4 Treatment blinding

This is a partial blind study: subjects, investigator staff, persons performing the assessments, and data analysts will remain blind to the identity of study treatments at the time of randomization and during the double-blind treatment period according to the specifications provided in [Appendix 4](#). Randomization data are kept strictly confidential until the time of unblinding for the respective person(s) with the following exceptions:

- The pharmacist charged with preparing and distributing infusion solutions containing VAY736 or placebo
- The medical monitor/Investigator at the site, independent to the study, who will review the hematology panel including differentials results throughout the study
- The unblinded monitor source data verifying the hematology panel and monitoring drug accountability

The PK bioanalyst will be unblinded during the clinical study, but will not provide individual PK data prior to data-base lock, except in case of an interim analysis happening after all patients have completed Week 24 and all team members, investigators and patients have been unblinded.

In order to help reduce the risk of unblinding that might arise if an infusion reaction occurs, all patients will receive treatment with paracetamol/acetaminophen and a H1 receptor blocker prior to infusion with VAY736.

An unblinded pharmacist at the investigator site will prepare the study treatment for infusion from the bulk open-labeled supplies. The diluent (dextrose 5% in water solution) serves as placebo and will not contain VAY736.

the hematology laboratory evaluation results will be concealed from the Investigators and patients in order to maintain the study blind. The necessary safety review may lead to the Novartis study team being inadvertently unblinded, however this information will not be communicated to the investigator.

Investigators and patients will be unblinded to treatment assignment after Week 24 (or earlier see [Section 5.5.8](#)) visit in order to propose open-label administration of VAY736 to the placebo arm.

Further unblinding will only occur in the case of subject emergencies (see [Section 5.5.12](#)), at the time of the interim analysis and at the conclusion of the study.

Further information regarding blinding (and unblinding) is presented in [Appendix 4](#).

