5.5.4 Instructions for prescribing and taking study treatment

The study medication VAY736 will be administered as an i.v. infusion over approximately 2 hours by the study center personnel following the instructions and using the material as described and specified in the VAY736 Pharmacy Manual.

Any update to the Pharmacy Manual describing the preparation of additional doses will be provided as needed directly to the study center personnel.

Presence of a physician at the patient bedside will be expected during the infusions. Unless performing a study assessment, patients should rest quietly for the next 2 hours under medical observation.

All dosages prescribed and dispensed to the subject and all dose changes during the study must be recorded on the Dosage Administration Record (e)CRF.

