6.4 Efficacy / Pharmacodynamic assessments

6.4.1 Pemphigus Disease Area Index (PDAI)

The PDAI is a specific cutaneous and mucosal disease activity assessment performed by the investigator based on the evaluation of lesions in well-defined anatomical locations ([Pfützte et al 2007](#); [Murrell et al 2008](#); [Rosenbach et al 2009](#); [Daniel et al 2012](#)).

The score is weighted for the number and size of lesions with a score of 0 (absent) to 10 given for skin (12 body locations), scalp and mucous membrane showing disease activity (erosions/blisters or new erythema). To be more precise at the lower end of the PDAI score the value of 1 that included 1-3 lesions on each anatomic region is split in intervals: 1 corresponds to one lesion (none greater than 2 cm); 1.3 corresponds to two lesions and 1.6 corresponds to three lesions.

Damage, such as post inflammatory hyperpigmentation or erythema from resolving lesion, is scored separately from the main score as absent (0) or present (1) for each body area or scalp resulting in a score of 0 to 12 or 0 to 1, respectively.

Therefore the PDAI score ranges from 0 to 263, with 250 points representing disease activity (120 points for skin activity; 10 points for scalp activity; 120 points for mucosal activity) and 13 points representing disease damage. Please refer to the PDAI scoring sheet in [Section 18-Appendix 6](#).

The investigator will complete a paper copy of the scale, which will serve as source data and the subject's responses will be transcribed into the CRF.

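### Protocol 5.1.1, 5.5.3.1 and 5.5.4 leave vial stock, the dispensing ledger and dose records within reach of the Investigator whom 5.4 and Table 16-1 keep blind

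*Protocol*

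**What the plan says.** **Text that brings the Investigator to the drug and its records**

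- Section 5.1.1 has the open-label bulk vials supplied to the Investigator.
- Section 5.5.3.1 has the stock received by a designated person and "kept in a secured location to which only the Investigator and designated staff have access". On the ledger it says: "The unblinded pharmacist and Investigator are accountable for ensuring maintenance of an accurate record of the shipment and dispensing of study drug". At study end, or during the study if that is allowed (an unblinded monitor is one of its examples), "the Investigator will provide a copy of the drug accountability ledger to the Monitor".
- Section 5.5.4: "All dosages prescribed and dispensed to the subject and all dose changes during the study must be recorded on the Dosage Administration Record (e)CRF". Section 6.3 repeats that dispensed doses go on the Dosage Administration Record, and names date and time of administration for the eCRF section. Under 8.2, designated investigator staff complete the eCRF.

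**Text that keeps the Investigator blind**

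- Section 5.4: "subjects, investigator staff, persons performing the assessments, and data analysts will remain blind to the identity of study treatments", at randomization and through the double-blind period. The listed exceptions are the pharmacist who prepares infusions, a haematology reviewer independent of the study, and the unblinded monitor, whose tasks include drug accountability.
- Table 16-1 marks the Primary Investigator and Treating Physician as blinded at allocation and administration.
- Section 5.5.2 sends the vials and a copy of the randomization list to the unblinded pharmacist or technician.

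**Why the records are informative**

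- Section 5.1.1: "The placebo control selected for this study is the 5% dextrose solution in the infusion bag". VAY736 comes in 150 mg vials.
- Section 5.5.2: "Appropriate documentation of the subject specific dispensing process must be maintained".
- Section 6.4.1 describes the PDAI as a "specific cutaneous and mucosal disease activity assessment performed by the investigator".

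**The concern.** The two groups of sections assign conflicting roles. One makes the Investigator a custodian of open-label stock and jointly answerable for a record of what was dispensed. The other keeps the same person blind and gives no exception for drug accountability. By reserving accountability checks for an unblinded monitor, the protocol itself treats these records as unblinding.

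The Investigator scores the PDAI, from which the primary variable is taken, and completes the IGA, the ABSIS and the disease-activity phase. The Investigator also takes part in decisions on standard-of-care increases (5.5.8) and taper (5.5.5), and adverse events are recorded with their relationship to treatment (7.1). Knowledge of allocation could influence any of these. Planned unblinding is at Week 24, and no earlier than the Week 12 visit for patients with a second standard-of-care increase (5.5.8). The route is therefore open during the period that feeds the Week 12 primary comparison, which sets 9 patients per dose against 6 on placebo.

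**Working it through.** **1. The plan's own figure.** Inputs: 9 vs 6 patients and SD 8 (Protocol 9.6). The success criteria (synopsis, data analysis) are a difference of at least 10 points with 50% evidence and any difference with 90% evidence, under non-informative priors.

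- SE = 8 × √(1/9 + 1/6) = 4.216.
- The 90% criterion needs an estimate of at least 1.2816 × 4.216 = 5.40. The 50% criterion needs at least 10, so the second one binds.
- P(success | d) = Φ((d − 10)/4.216).
- d = 0: 0.89% (stated: under 1%). d = 6: 17.1% (stated: below 20% for differences under 6). d = 14: 82.9% (stated: approximately 80%).

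A simulation with estimated SD (13 degrees of freedom) gives 0.87%, 17.2% and 82.9%. The stated figures stand. They presuppose unbiased scoring.

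**2. Who holds what**

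| Item | Points to the Investigator or site staff | Points to unblinded roles |
|---|---|---|
| Receipt of vials | 5.1.1: Investigator | 5.5.2: unblinded pharmacist or technician |
| Storage access | 5.5.3.1: Investigator and designated staff | none stated |
| Ledger | 5.5.3.1: Investigator, jointly | 5.5.3.1: unblinded pharmacist, jointly |
| Ledger handover | 5.5.3.1: Investigator | none stated |
| Accountability check | none | 5.4 and 5.5.3.1: unblinded monitor |
| Dispensed dose | 5.5.4 with 8.2: (e)CRF, site staff | none stated |

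No sentence supplied removes the stock, ledger or dose record from the blinded Investigator.

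**3. Would a dispensing record identify the arm?** Inputs: 150 mg labelled content (Table 5-1), weight 40–150 kg (4.1), doses of 3 and 10 mg/kg. Assumption: whole vials, counted at labelled content. Vials = ⌈3w/150⌉ = ⌈w/50⌉ for 3 mg/kg and ⌈10w/150⌉ = ⌈w/15⌉ for 10 mg/kg. Placebo uses 0.

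| Weight (kg) | 3 mg/kg | 10 mg/kg | Gap |
|---|---|---|---|
| 40–45 | 1 | 3 | 2 |
| >45–50 | 1 | 4 | 3 |
| >50–60 | 2 | 4 | 2 |
| >60–75 | 2 | 5 | 3 |
| >75–90 | 2 | 6 | 4 |
| >90–100 | 2 | 7 | 5 |
| >100–105 | 3 | 7 | 4 |
| >105–120 | 3 | 8 | 5 |
| >120–135 | 3 | 9 | 6 |
| >135–150 | 3 | 10 | 7 |

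The smallest gap is 2 vials, and placebo never shares a count with an active arm. A count of 3 alone could be either dose, but body weight, which the site measures at baseline, settles it. Before the safety review only 3 mg/kg and placebo are in use (5.2), so any vial use means active.

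**4. Can the record be tied to a patient?** Yes, if it is kept per subject, as 5.5.2 requires of dispensing documentation. Section 5.5.3.1 does not list the ledger's columns. Even dated stock movements would often suffice, because 3.1 bars parallel infusions at one centre.

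**5. Illustration only.** The documents give no scoring bias. If PDAI scoring favoured active by b points on average over the whole comparison, the false-positive chance would be Φ((b − 10)/4.216): b = 1, 1.6%; b = 2, 2.9%; b = 3, 4.8%; b = 4, 7.7%.

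**The case against.** The strongest reply is that being accountable for a record is not the same as writing or reading it. An Investigator can discharge the duty through an unblinded delegate. Section 5.5.3.1 allows for this: a designated person receives the drug, designated staff have access, and returns fall to the Investigator or a designee after sponsor authorization, with the site pharmacist as one route for destruction. The default time for the ledger handover is study end, when Week 12 scores can no longer change. Storage and preparation rules sit in a Pharmacy Manual that was not supplied and may restrict access. On the eCRF, 6.3 names only date and time of administration, and 5.5.12 keeps the unblinded code off the CRF, though in the context of emergency unblinding.

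Most of this stands, and it rules out several readings that a reader might infer:

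- *No site can follow 5.5.3.1 and keep the blind.* Not shown, since delegation can reconcile the two.
- *The ledger discloses every patient's arm.* Not shown. Its columns are not specified, bulk labels carry no subject information, and an Investigator would see only local patients.
- *The true false-positive chance exceeds the stated figure.* Not shown. The bias values are assumed, and they apply to the average over all sites and patients.
- *Past allocations let the Investigator predict later ones.* Speculative. A sponsor designee issues numbers centrally, and no block size is given.

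The conflict between sections remains. One could read the word unblinded in 5.5.3.1 as covering the Investigator too. The only unblinded Investigator defined is the haematology reviewer, who is given no accountability role and is marked blinded at allocation and administration in Table 16-1. Elsewhere 5.5.3.1 uses the title without qualification. The handover clause also gives an unblinded monitor, which this trial has, as an example of when handover during the study may be allowed.

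**Conclusion.** The point holds as a conflict of role assignments that leaves open a route to unblinding. Sections 5.1.1, 5.5.3.1 and 5.5.4 place vials, ledger and dose data with the Investigator or site staff. Sections 5.4, 5.5.2 and Table 16-1 require the opposite.

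A subject-level dispensing or dose record would reveal allocation with certainty under whole-vial dispensing: 0 vials for placebo, 1–3 for 3 mg/kg, 3–10 for 10 mg/kg, and a gap of at least 2 between doses at a given weight. The exposure is limited to patients at that Investigator's site and exists before the Week 12 assessment.

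It would be wrong to conclude that the blind was or must be broken, or that the design's error rate is misstated. The figure of under 1% reproduces at 0.89%, and the 1.6% to 7.7% range rests wholly on an assumed average bias of 1 to 4 points. In a non-confirmatory trial this is a correction worth making because it is cheap and protects an investigator-scored primary endpoint.

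**What to change.** - **5.1.1 and 5.5.3.1:** assign receipt, storage access, the ledger, returns and ledger handover to the unblinded pharmacist or an unblinded designee. Only the unblinded monitor reviews the ledger. State that the blinded Investigator and staff have no access to vials, store or ledger until all patients at that site are unblinded.
- **5.5.4 and 6.3:** blinded staff enter only infusion date, times, volume and interruptions. The mg dose and vial count stay in the unblinded pharmacy record until unblinding.
- **5.5.2 and Table 16-1:** align both with the above. As supplied, the table has no row for the site pharmacist; add one.
- **Pharmacy Manual:** check that its access rules agree.

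Cost: a wording amendment and a change to site delegation. The unblinded pharmacist and monitor already exist, and sample size and analysis are untouched. The downside is that, until unblinding, the Investigator oversees accountability through the unblinded delegate.

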5.5.3.2 Handling of other study treatment

Pre-medication

In order to reduce the chance of infusion reactions and subsequent potential unblinding, patients will be administered paracetamol/acetaminophen and a H1 receptor blocker before the infusion. Details are given in [Section 5.1.2.1](#). Use of pre-medication will be monitored.

Standard of Care (SoC) medications

Following treatment on Day 1 with study medication, SoC medications are to be maintained at a stable dose level until "disease control" in signs/symptoms of PV. Limited changes to a patient's dose of SoC medications will be allowed. Details are given in [Section 5.5.5](#).

Use of SoC medication will be monitored.

The medications needed for pre-medication and allowed for treatment of adverse reactions and PV SoC medications are not considered study supplies and therefore need to be supplied by the study site or treating physician.

5.5.4 Instructions for prescribing and taking study treatment

The study medication VAY736 will be administered as an i.v. infusion over approximately 2 hours by the study center personnel following the instructions and using the material as described and specified in the VAY736 Pharmacy Manual.

Any update to the Pharmacy Manual describing the preparation of additional doses will be provided as needed directly to the study center personnel.

Presence of a physician at the patient bedside will be expected during the infusions. Unless performing a study assessment, patients should rest quietly for the next 2 hours under medical observation.

All dosages prescribed and dispensed to the subject and all dose changes during the study must be recorded on the Dosage Administration Record (e)CRF.

5.5.5 Taper of Standard of Care (SoC) medications

Following treatment on Day 1 with study medication, SoC medications are to be maintained at a stable dose level until disease control in signs/symptoms of PV. Limited changes to a patient's dose of SoC medications will be allowed as described in the following paragraphs.

Control of disease activity or "disease control" is defined as the time at which new lesions cease to form and established lesions begin to heal ([Murrell et al 2008](#) – see [Section 6.4.4](#)).

Once disease control is achieved, as defined above, a patient's dose of SoC medications are to be kept stable for a minimum of 2 weeks and at the end of this period if no new lesions have developed and the majority (~80%) of lesions have healed, the patient will begin a protocol-defined corticosteroid taper to safely deliver the patient to the lowest dose needed to maintain control of their PV.

- If a patient reached disease control between protocol-defined study visits, ad-hoc unplanned clinic visits or consultation over the phone is possible to review/alter a patient's steroid dose
- Ad-hoc unplanned clinic visits or consultations with a patient over the phone are also possible during the SoC medication taper, at the discretion of the investigator (e.g., evaluate worsening of disease or adjust dose)

The prednisone will be tapered according to the following instructions:

- reduce the daily dose by 20 mg every week until reaching a daily dose of 40 mg,
- reduce the daily dose by 10 mg every week from a daily dose of 40 mg down to 10 mg,
- once the daily dose of 10 mg has been reached, the taper will be determined by the investigator.

If the patient has been placed on steroids as short-term treatment and the prednisone can be safely discontinued the following week, then this is recommended. If the patient has been on steroids chronically and will require a slower taper after reaching 10 mg/day then the investigator should consider decreasing the dose to 5 mg the following week with the remaining taper to be determined by the patient's response. At each visit after initiating the steroid taper, a patient is eligible to continue with a steady decrease in their steroid dose if disease control continues and no evidence of steroid withdrawal is observed (e.g., fatigue, weakness, nausea, anorexia, hypotension, body aches or joint pain). Dose adjustments as required by the steroid taper will take place weekly, regardless of the visit schedule, and in the event that patients require consultation with the investigator this can take place as an ad-hoc unplanned visit or telephone conversation.

If a patient has worsening symptoms or evidence of steroid withdrawal then the patient is considered to have failed their taper and the steroid dose will either be maintained or increased to the minimum dose considered adequate by the investigator to control the patient's symptoms (e.g., the previous dose that was tolerated and offered control of PV disease activity – see [Section 5.5.8](#)). In the event that a patient fails the protocol defined tapering regimen multiple times, then the investigator can introduce a tapering regimen to safely bring the patient to the lowest amount of SoC medication as quickly as possible.

A taper of SoC medication adjuvant to oral corticosteroid (e.g., MMF or azathioprine) is to be started only after the steroid dose has been successfully decreased such that it is approximately 5 mg per day or less and has been maintained at this level for one month. Azathioprine or mycophenolate mofetil are to be tapered such that the dose is decreased by approximately 25% every 4 weeks. Changes to such medication dose/regimen are preferred at protocol-defined or ad-hoc study visits rather than by consultation with a patient over the phone (as was possible for steroid tapering).

